6.10.2.2. Compliance to Insulin Glargine (U100)

Compliance to insulin glargine (U100) will be defined as taking at least 75% of the scheduled insulin glargine (U100) injections. Compliance will be calculated by the formulas below:

Overall Insulin compliance (%) = $\frac{\text{total # of injections expected} - \text{total # of missed injections}}{\text{total # of injections expected}} * 100$.

Treatment compliance will be summarized descriptively for mITT population during Study Period 2.

Information related to compliance to treat-to-target algorithm including number of assessments performed correctly, number of assessments that required a dose change, number of assessments for which the outcomes were correctly followed by the patient, and reasons for non-compliance will be summarized for Study Period 2.

6.10.2.3. Compliance to Insulin Lispro (U100)

Compliance to insulin lispro (U100) will be defined as taking at least 75% of the scheduled insulin lispro (U100) injections. Compliance will be calculated by the formula below:

Overall Insulin compliance (%) = $\frac{\text{total # of injections expected} - \text{total # of missed injections}}{\text{total # of injections expected}} * 100$.

Treatment compliance will be summarized descriptively for the insulin lispro (U100) arm during Study Period 2.

Information related to compliance to treat-to-target algorithm including number of assessments performed correctly, number of assessments that required a dose change, number of assessments for which the outcomes were correctly followed by the patient, and reasons for non-compliance will be summarized for Study Period 2.

6.11. Important Protocol Deviations

Important protocol deviations are identified in the Trial Issues Management Plan (TIMP). A listing and a summary of important protocol deviations will be provided for the randomized population by treatment. If applicable, a separate listing of important protocol deviations will be provided for the enrolled population.

6.12. Efficacy Analyses

Potentially for regulatory agencies, primary and key secondary efficacy assessments will be guided by the “treatment-regimen” estimand conducted using the FAS. Assessment of the primary and secondary efficacy objectives subject to type 1 error rate control (key secondary) will be conducted with multiple imputation of missing data (see Section 6.12.1.3) at 52 weeks. For publications and other purposes, the assessment of efficacy objectives will be guided by the “efficacy” estimand using the EAS without imputation of missing data.

Unless specified otherwise, the treatment term will include tirzepatide 5 mg, 10 mg, and 15 mg and insulin lispro (U100). The efficacy of the pooled tirzepatide arms compared with insulin lispro (U100) will be estimated via a linear contrast which averages the effect sizes of individual tirzepatide doses compared with insulin lispro (U100).

6.12.1. Primary Efficacy Analysis

The primary efficacy measure will be change in HbA1c from baseline (postbaseline – baseline). Both HbA1c values as well as change from baseline in HbA1c will be summarized by treatment (pooled cohort of tirzepatide doses and insulin lispro) and nominal visit (week).

6.12.1.1. Primary Analysis Relative to the Efficacy Estimand

The primary analysis relative to the “efficacy” estimand will be conducted using HbA1c data in the EAS from baseline through the 52-week visit with the aid of an MMRM. Restricted maximum likelihood (REML) will be used to obtain model parameter estimates and the Kenward-Roger option will be used to estimate denominator degrees of freedom. The response variable of the MMRM model will be the primary measure and model terms of interest will include treatment (5 mg, 10 mg, and 15 mg tirzepatide and insulin lispro [U100]), visit, treatment-by-visit interaction, country/pooled country, and baseline metformin use (Yes/No) as fixed effects, and baseline HbA1c as a covariate. A linear contrast, averaging estimates from the individual tirzepatide doses at 52 week visit, will be used to estimate the treatment effect of the combined tirzepatide arms compared with insulin lispro (U100). An unstructured covariance matrix will be used to model the within-patient errors. If this model fails to converge, the following covariance structures will be tested in order:

- Heterogeneous Toeplitz
- Heterogeneous First Order Autoregressive
- Heterogeneous Compound Symmetry
- Toeplitz
- First Order Autoregressive, and
- Compound Symmetry.

The first covariance structure that converges will be used. The resulting least squares mean (LSM) estimate of mean change from baseline in HbA1c will be summarized by visit and by study treatment (ie, the pooled cohort of tirzepatide doses and insulin lispro [U100]).

With the aid of the MMRM analysis, 2-sided 95% confidence interval (CI) for mean change in HbA1c from baseline to the 52-week visit will be derived and summarized for the combined tirzepatide doses compared to insulin lispro (tirzepatide – insulin lispro). If the upper limit of the CI is $\leq 0.3\%$, then the pooled cohort of tirzepatide doses will be declared noninferior to insulin lispro (U100) relative to change in HbA1c from baseline.

6.12.1.2. Primary Analysis Relative to the Treatment-Regimen Estimand

The primary analysis relative to the treatment-regimen estimand will be conducted utilizing HbA1c data in the FAS at baseline and at the 52-week visit with the aid of an analysis of covariance (ANCOVA) model. The response variable will be the primary measure and model terms will include treatment (5 mg, 10 mg, and 15 mg tirzepatide and insulin lispro), country/pooled country, and baseline metformin use (Yes/No) as fixed effects and baseline

HbA1c as a covariate. A linear contrast, averaging estimates from the individual doses, will be used to estimate the treatment effect of the combined tirzepatide arms compared with insulin lispro (U100). The ANCOVA analysis will be conducted using multiple imputation of missing primary measures (see Section 6.12.1.3 for details) and statistical inference over multiple imputation of missing data guided by Rubin (1987).

With the aid of the ANCOVA analysis, 2-sided 95% CI for mean change in HbA1c from baseline to the 52-week visit will be derived and summarized for the combined tirzepatide doses compared to insulin lispro (tirzepatide – insulin lispro). If the upper limit of the CI is $\leq 0.3\%$, then the pooled cohort of tirzepatide doses will be declared noninferior to insulin lispro (U100) relative to change in HbA1c from baseline.

6.12.1.3. Methods for Multiple Imputations

For efficacy analyses relative to the “treatment-regimen” estimand, missing HbA1c data at the 52-week visit will be imputed based on “retrieved dropouts,” defined as patients who had their HbA1c value measured at the 52-week visit in the same treatment arm who prematurely discontinued study drug. In cases where there are not enough retrieved dropouts to provide a reliable imputation model (ie, model implemented by the SAS program does not converge), an alternative multiple imputation method with reference to the baseline data (“return to baseline” approach) will be used as the primary analysis relative to the treatment-regimen estimand. If value of imputed HbA1c change from baseline is $<-6.0\%$ or $>6.0\%$, that value will be set to -6.0% or 6.0%, respectively, to avoid unrealistic imputed values. Analyses will be conducted with multiple imputations, and statistical inference over multiple imputations will be guided by the method proposed by Rubin (1987).

Imputation of missing data using retrieved dropouts may bias towards the null which favors the noninferiority outcome. A sensitivity analysis using imputation under the non-inferiority null hypothesis will also be conducted to address this limitation (Koch 2018). In this analysis, missing data will first be imputed using retrieved dropouts from each arm. Since larger negative values represent better response for HbA1c reduction, the noninferiority margin of 0.3% will be added to the imputed values in the tirzepatide arms. This approach helps to avoid bias in the direction of making tirzepatide and insulin lispro arms more similar, therefore it reduces the chance of incorrectly demonstrating noninferiority.

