9.4.3. Efficacy Analyses

9.4.3.1. Primary Analyses

As indicated in Section 9.4.1., there will be 2 primary efficacy analyses conducted to establish noninferiority of the pooled cohort of tirzepatide at 5 mg, 10 mg, and 15 mg to insulin lispro (U100) relative to mean change in HbA1c from baseline to the 52-week visit.

The primary efficacy analysis regarding the “treatment-regimen” estimand, defined in Section 9.4.1., will analyze change in HbA1c values obtained at the 52-week visit using an ANCOVA with terms of treatment, country, metformin use (Yes or No), and baseline HbA1c as a covariate. Missing change in HbA1c from baseline values at the 52-week visit will be imputed based on observed changes in HbA1c from baseline values at the visit from participants in the same treatment arm who had their efficacy assessed after early discontinuation of study intervention and/or initiation of rescue antihyperglycemic medication. Analysis will be conducted with multiple imputations, and statistical inference over multiple imputations will be guided by the method proposed by Rubin.³³

The ANCOVA analysis will report least square means and standard error values for the pooled cohort of tirzepatide doses and insulin lispro (U100) as well as the difference in mean change in HbA1c from baseline to the 52-week visit. Two-sided 95% CI for the difference in mean change in HbA1c from baseline to 52-week visit between the pooled cohort of 5 mg, 10 mg, and 15 mg tirzepatide and insulin lispro (U100) will be constructed. The mean change in HbA1c from baseline to the 52-week visit will be calculated as subtracting the baseline HbA1c from the 52-week HbA1c. The difference between the pooled tirzepatide cohort and insulin lispro (U100) will be calculated as subtracting the mean change in HbA1c for insulin lispro (U100) from the mean change of HbA1c for the pooled tirzepatide cohort. If the upper limit of the CI is below 0.3%, the pooled cohort of 5 mg, 10 mg, and 15 mg QW tirzepatide will be declared noninferior to insulin lispro (U100).

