5.2. Sample Size Determination

Although the primary objective of the trial is to demonstrate that the pooled cohort of tirzepatide (5 mg, 10 mg, and 15 mg) QW is noninferior to insulin lispro (U100) TID, relative to the primary endpoint (mean change in HbA1c from baseline to 52 weeks), sample size selection is guided by establishing noninferiority of each tirzepatide dose, tested against insulin lispro (U100), relative to the primary endpoint (mean change in HbA1c from baseline to 52 weeks). The power is assessed based on the following assumptions:

- the evaluation of noninferiority of each individual tirzepatide dose to insulin lispro (U100) will be conducted at one-sided 0.025 significance level, using a two-sample t-test
- a 0% difference in mean change in HbA1c from baseline to 52 weeks for each tirzepatide arm compared with insulin lispro (U100)
- a common standard deviation (SD) of 1.3% (accounting for increase in SD due to the inclusion of data on rescue medications and after premature treatment discontinuation and imputation of missing data)
- a noninferiority margin of 0.3%, and
- 1:1:1:3 randomization ratio (chosen to optimize power for establishing primary objective and to optimize safety comparison between pooled tirzepatide cohort versus insulin lispro).

On the basis of these assumptions, randomizing 1182 participants in a 1:1:1:3 ratio to tirzepatide 5 mg (197 participants), tirzepatide 10 mg (197 participants), tirzepatide 15 mg (197 participants) and insulin lispro (U100) (591 participants) provides 80% power to demonstrate noninferiority of each tirzepatide dose to insulin lispro (U100). Furthermore, this sample size will ensure 97% power to achieve the primary objective: establishing noninferiority of the pooled cohort of tirzepatide (5 mg, 10 mg, and 15 mg) compared to insulin lispro (U100), using a 2-sample t-test at 1-sided significance level of 0.025, provided a 0.0% difference in mean change in HbA1c from baseline to 52 weeks for the pooled cohort of tirzepatide doses compared with insulin lispro (U100), a common SD of 1.3% and noninferiority margin of 0.3%.

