6.17.4. Study Visits

A summary of patients with study visit impacted by COVID-19/ related restrictions will be provided by treatment group. In this table, number and proportion of patients missing study visit including primary endpoint visit will be summarized.

7. Unblinding Plan

Even though GPHD is an open-label study, the study team will remain as blinded as possible to the tirzepatide doses. The unblinding plan will be located in a separate document.

8. References

Koch GG. Comments on 'Current issues in non-inferiority trials' by Thomas R. Fleming, Statistics in Medicine. DOI: 10.1002/sim.2855. *Stat Med*. 2008;27(3):333-342. <https://doi.org/10.1002/sim.2923>

Maruish ME, editor. *User's Manual for the SF-36v2 Health Survey*. 3rd ed. QualityMetric Incorporated; 2011.

Protocol I8F-MC-GPHD A Randomized, Phase 3, Open-label Trial Comparing the Effect of the Addition of Tirzepatide Once Weekly versus Insulin Lispro (U100) Three Times Daily in Participants with Type 2 Diabetes Inadequately Controlled on Insulin Glargine (U100) with or without Metformin (SURPASS-6).

Rubin DB. *Multiple imputation for nonresponse in surveys*. John Wiley & Sons Inc.; 1987.

9. Appendices

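### In the treatment-regimen analysis, participants still on study drug who miss the Week 52 measurement are imputed from participants who stopped drug

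*SAP*

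**What the plan says.** SAP 6.12.1.3 sets the rule for the treatment-regimen estimand: "missing HbA1c data at the 52-week visit will be imputed based on" retrieved dropouts, meaning participants in the same arm who stopped study drug early but have a Week 52 HbA1c. SAP 6.4 sends all participants with a missing Week 52 value to this method for the primary and type-1-controlled secondary endpoints. Neither section separates those still taking study drug. If the model does not converge, return-to-baseline imputation becomes the primary analysis for this estimand. Body weight (6.12.2.2) and HbA1c <7% (6.12.2.3) refer back to the same approach.

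Protocol 9.4.3.1 takes its donors from "participants in the same treatment arm who had their efficacy assessed after early discontinuation of study intervention" and/or after starting rescue. The SAP narrows this to those who stopped drug, and its revision history lists the change.

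The SAP acknowledges a possible bias: "Imputation of missing data using retrieved dropouts may bias towards the null which favors the noninferiority outcome". It adds a sensitivity analysis that raises imputed tirzepatide values by the 0.3% margin. Noninferiority itself is declared from the primary ANCOVA interval (6.12.1.2). Missed Week 52 visits are foreseen in the COVID-19 section (6.17.4), where the "number and proportion of patients missing study visit including primary endpoint visit will be summarized".

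The other primary analysis, for the efficacy estimand, is a repeated-measures model under missing at random and does not use this rule (6.4, 6.12.1.1).

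**The concern.** The treatment-regimen estimand asks for the Week 52 outcome whatever the adherence. For a participant who stopped drug, that outcome is off-drug, and retrieved dropouts are sensible donors. For a participant who is still injecting and misses the visit, it is an on-drug outcome. The rule gives that participant an off-drug value, or a baseline-referenced one under the fallback. It also names no role for that participant's earlier HbA1c, which the Schedule of Activities collects at Weeks 4, 8, 12, 16, 20, 24 and 40.

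Whether this moves the comparison depends on how the off-drug arms compare. There is reason to expect them to be more alike than the on-drug arms. After stopping, both arms continue glargine titration and may add another agent (Protocol 7.1), and Table 10 note d allows insulin lispro in the tirzepatide arms as rescue or after discontinuation. In that case the estimated difference is pulled towards zero. At stake are the noninferiority error rate if tirzepatide is truly worse, and the size of the superiority estimates if it is better.

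**Working it through.** **Inputs from SAP 5.2.** Margin 0.3, SD 1.3, arms 197/197/197/591, assumed difference 0, and the pooled test done "using a 2-sample t-test at 1-sided significance level of 0.025".

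**Inputs the documents do not give.** The share missing at Week 52, the share of retrieved dropouts, and donor means. All values used for these are assumptions.

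**1. Reproduce the plan's power.**
- Pooled: SE = 1.3 × √(1/591 + 1/591) = 0.0756. Power = Φ(0.3/0.0756 − 1.96) = 97.8%. The plan says "this sample size will ensure 97% power to achieve the primary objective".
- Each dose: SE = 1.3 × √(1/197 + 1/591) = 0.1069. Power = Φ(0.3/0.1069 − 1.96) = 80.1%, against 80% stated.

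The framework agrees with the plan.

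**2. Direction.** Let a share m of each arm be missing while on drug, with between-arm differences D_on and D_off. The rule puts m × D_off where m × D_on belongs, a shift of m × (D_off − D_on). It is zero if the two differences are equal. With D_on = 0.3 and D_off = 0, the estimate becomes 0.3 × (1 − m): 0.291, 0.285 and 0.270 at m = 3%, 5% and 10%. Holding the SE at 0.0756, Φ(0.3m/0.0756 − 1.96) gives 3.3%, 3.9% and 5.9%. This is only a rough guide, because it leaves out the variance that imputation adds.

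**3. Simulation of the planned method.** Retrieved-dropout multiple imputation was combined by Rubin's rules, with 30 imputations, 2,500 runs, planned arm sizes and imputed changes capped at ±6.0. The true difference is +0.3, donors are equal between arms, and the donor share equals the missing share. Monte Carlo error is about 0.3 to 0.4 percentage points.

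| Missing per arm | Of these, on drug | Mean estimate | One-sided error | Error with +0.3 added |
|---|---|---|---|---|
| 5% | all | 0.284 | 4.0% | 2.1% |
| 5% | half | 0.291 | 2.4% | 1.9% |
| 5% | none | 0.299 | 2.4% | 1.2% |
| 10% | all | 0.269 | 4.7% | 2.3% |
| 10% | half | 0.282 | 3.3% | 1.6% |
| 10% | none | 0.305 | 1.8% | 1.0% |

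The estimates agree with a mixture in which +0.3 is the overall treatment-regimen difference. With 10% donors and 10% missing on drug, the on-drug difference is 0.3/0.9 = 0.333. The rule then gives 0.8 × 0.333 = 0.267, against 0.269 simulated. At 5% it gives 0.9 × (0.3/0.95) = 0.284, as simulated. The matched case at 10% (none on drug) sits below 2.5%, so rows are better read against each other than as exact rates.

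**4. Other true differences.**
- At 0, mean estimates stay between −0.001 and 0.005, and the chance of declaring noninferiority is 93% to 96%, so nothing is gained.
- At −0.4 with all missing values on drug, the estimate shrinks to −0.378 (5% missing) or −0.351 (10%). The latter loses 0.049/0.4 = 12% of the effect.

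**The case against.** The other side has substance, and much of it stands.

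- **Scope.** A reader might infer that every missing Week 52 value in the trial is handled this way. It is not. The efficacy-estimand MMRM is untouched, and the efficacy-estimand HbA1c <7% analysis imputes from all available same-treatment data (6.12.2.3).
- **Direction.** A reader might infer that the rule always pulls the arms together and favours noninferiority. Donors come from the same arm, so convergence requires off-drug differences smaller than on-drug ones, and leniency requires tirzepatide to be truly worse. The SAP itself says only that bias may arise. Unequal missingness can act either way: with equal on-drug means and donors assumed 0.8 worse in both arms, 10% against 5% missing on drug shifts the difference by 0.8 × (0.10 − 0.05) = 0.04 against the arm with more missing.
- **Size.** The fixed-SE 5.9% at 10% missing is tempting to quote. Simulation with Rubin's rules gives 4.7%, and less when some missing values are off drug.
- **Few people affected.** Under Protocol 7.2, leaving the study also ends study drug, so withdrawals are correctly matched to retrieved dropouts. Protocol Appendix 9 allows mobile blood draws, local laboratory testing and a ±28-day window at Visit 23. SAP 6.17 lists analyses that may be done, which is not a forecast of many missed visits.
- **Already addressed.** The SAP discloses the bias, and its +0.3 analysis restores about 2.5% in the scenario tested.

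The last point is the strongest, but it leaves gaps. Noninferiority is declared from the uncorrected interval, and no rule says what follows if the two analyses disagree. The +0.3 step is described only for retrieved-dropout imputation, not for the fallback. The superiority tests for HbA1c, weight and HbA1c <7% get no equivalent remedy.

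**Conclusion.** The mismatch between donor and recipient is in the text and is confined to the treatment-regimen analysis. Under the assumptions stated (true difference at the margin, equal off-drug arms, all missing values on drug), pooled one-sided error rises from 2.5% to about 4.0% at 5% missing and 4.7% at 10%. At 10% missing it is 3.3% when half are on drug, and there is no inflation when none are. At the planned 0% difference there is no material shift. If tirzepatide is better, the effect is diluted, which is conservative for superiority but understates the estimate.

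The documents do not support reading this as a general bias towards noninferiority, or as one the SAP ignored. It is a limited defect with a simple remedy, worth correcting because this estimand is the one SAP 6.12 earmarks for regulatory agencies.

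**What to change.** In SAP 6.12.1.3, split missing Week 52 values by study-drug status at Week 52:

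- **Off drug, including study withdrawals:** impute from retrieved dropouts of the same arm, as now.
- **Still on drug:** impute from on-drug participants of the same arm, using baseline and earlier post-baseline values.

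Apply the same split to body weight and HbA1c <7% under this estimand. Keep the +0.3 sensitivity analysis, and state how it bears on the noninferiority conclusion if it disagrees with the primary result.

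The cost is SAP wording and a second imputation model. The earlier HbA1c values are already collected, and 6.12.2.3 already specifies fully conditional imputation for the efficacy estimand. The downside is a missing-at-random assumption within the on-drug group; if it holds, the step 2 estimate returns to 0.300 and the error to 2.5%. This is a cheap improvement.

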- Any other TEAE, SAE, or clinically significant laboratory value for which the investigator believes that permanent study intervention discontinuation is the appropriate measure to be taken
- If a participant misses 3 or more consecutive doses of tirzepatide due to intolerable GI symptoms (that is, nausea, vomiting, or diarrhea) that could be reasonably attributed to tirzepatide, despite following the mitigation steps per Section 6.6.3.
- If female participant becomes pregnant (see Section 8.3.5.)

Note: Participant will be discontinued from the study, as well.

- If a participant is diagnosed with T1DM

Note: Participant will be discontinued from the study, as well.

Participants who permanently stop tirzepatide or insulin lispro (U100) will continue to titrate insulin glargine (U100) and receive another glucose-lowering intervention, if needed per clinical judgment of investigator, and will continue participating in the trial according to the protocol to collect all planned efficacy and safety measurements.

Participants discontinuing tirzepatide or insulin lispro (U100) prematurely for any reason should complete AE and other follow-up procedures per this protocol.

See Section 1.3. for data to be collected at the time of intervention discontinuation and follow-up and for any further evaluations that need to be completed.

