7.2. Participant Discontinuation/Withdrawal from the Study

A participant may withdraw from the study

- at any time at his or her own request
- at the request of his or her designee, for example, parents or legal guardian
- at the discretion of the investigator for safety, behavioral, compliance, or administrative reasons
- if enrollment in any other clinical study involving an investigational product or enrollment in any other type of medical research judged not to be scientifically or medically compatible with this study, or
- if the participant, for any reason, requires treatment with another therapeutic agent that has been demonstrated to be effective for treatment of the study indication, discontinuation from the study occurs prior to introduction of the new agent.

A participant will be withdrawn from the study:

- if a female participant becomes pregnant
- if a participant is diagnosed with T1DM.

Discontinuation is expected to be uncommon.

At the time of discontinuing from the study, if possible, an early termination visit should be conducted, as shown in the SoA. See Section [1.3](#). for data to be collected at the time of study

discontinuation and follow-up and for any further evaluations that need to be completed. The participant will be permanently discontinued both from the study intervention and from the study at that time.

If the participant withdraws consent for disclosure of future information, the sponsor may retain and continue to use any data collected before such a withdrawal of consent. If a participant withdraws from the study, he or she may request destruction of any samples taken and not tested, and the investigator must document this in the site study records.

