6.12.2. Secondary Efficacy Analyses Subject to Type 1 Error Rate Control

6.12.2.1. Mean Change in HbA1c from Baseline at the 52 Week Visit

Noninferiority of individual doses of tirzepatide 5 mg, 10 mg, and 15 mg to insulin lispro (U100) will be conducted in the same manner as the primary analyses in Section 6.12.1, with individual doses of tirzepatide used in the treatment term.

Assessment of superiority of tirzepatide doses compared to insulin lispro (U100) will be conducted using the same statistical models as those used for evaluating the primary objective in Section 6.12.1. The treatment term will include tirzepatide 5 mg, 10 mg, 15 mg and insulin lispro

(U100). A linear contrast, averaging estimates from individual doses, will be used to assess the superiority of combined tirzepatide doses compared to insulin lispro (U100). Decisions will be guided by the 2-sided p-values for mean comparisons between tirzepatide doses and insulin lispro (U100) (see details in Section 6.12.3).

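### Does the noninferiority-null sensitivity analysis need its own return-to-baseline version in case the fallback imputation becomes primary?

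*SAP*

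**What the plan says.** For the treatment-regimen estimand, SAP 6.12.1.3 fills missing week-52 HbA1c from participants in the same arm who stopped study drug early but were still measured at week 52. If the SAS model does not converge, a multiple imputation that refers to baseline data "will be used as the primary analysis relative to the treatment-regimen estimand".

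The next paragraph of that section warns: "Imputation of missing data using retrieved dropouts may bias towards the null which favors the noninferiority outcome". It therefore adds one sensitivity analysis, in which "missing data will first be imputed using retrieved dropouts from each arm" and the 0.3% margin is then added to the imputed tirzepatide values. No version is written for return-to-baseline.

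SAP 6.12.1.2 declares noninferiority from the unshifted 95% confidence interval (upper limit at or below 0.3%). Under SAP 6.12.2.1, noninferiority of the individual doses "will be conducted in the same manner as the primary analyses in Section 6.12.1". The efficacy-estimand analysis in SAP 6.12.1.1 "will be conducted using HbA1c data in the EAS from baseline through the 52-week visit with the aid of an MMRM" and uses neither imputation.

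**The concern.** The first step of the sensitivity analysis is the very model whose failure triggers the fallback. Read literally, the check disappears in exactly the branch where return-to-baseline carries the treatment-regimen result.

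Return-to-baseline could need such a check too. If it centres imputed change on zero in both arms, it can pull the arms together, and in a noninferiority test that may favour tirzepatide. The tests affected would be the pooled hypothesis Hp,1, which opens the graphical testing scheme, and the dose-level hypotheses H5,1, H10,1 and H15,1. SAP 6.12 names the treatment-regimen estimand as the one potentially meant for regulators. Neither the SAP nor Protocol 9.4.3.1 specifies a tipping-point or other noninferiority-null analysis that would step in.

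**Working it through.** **Inputs from SAP 5.2:** margin 0.3%, SD 1.3%, one-sided level 0.025, 197 participants per tirzepatide dose (591 pooled), 591 on lispro.

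**Assumed, because the documents are silent:** missing fractions mT (tirzepatide) and mL (lispro) of 5% to 15%; mean lispro change of -1.2%; return-to-baseline draws centred on zero with SD 1.3%. The SAP says only that the method refers to baseline data.

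**1. The plan's own figures.** Power = Φ(0.3/SE - 1.960).
- Single dose: SE = 1.3 × √(1/197 + 1/591) = 0.10695, so Φ(2.805 - 1.960) = 80.1%, against 80% stated.
- Pooled: SE = 1.3 × √(2/591) = 0.07562, so Φ(3.967 - 1.960) = 97.8%, against 97% stated.

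**2. Bias of return-to-baseline.** Imputing zero drops the true mean change of the missing participants, so for tirzepatide minus lispro

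bias = mL × μL,miss - mT × μT,miss.

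A negative bias favours tirzepatide. The 0.3% shift adds 0.3 × mT.

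**3. Missing participants keep the full difference.** At the margin their means are -0.9% (tirzepatide) and -1.2% (lispro). At 10/10 missing, bias = 0.10 × (-1.2) - 0.10 × (-0.9) = -0.030. Pooled one-sided error comes from 60,000 simulated trials per case, with 20 imputations and Rubin's rules:

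| Missing, tirzepatide/lispro | Bias | Bias with shift | Error | Error with shift |
|---|---|---|---|---|
| 5%/5% | -0.015 | 0 | 3.0% | 1.7% |
| 10%/10% | -0.030 | 0 | 3.5% | 1.2% |
| 15%/15% | -0.045 | 0 | 4.4% | 0.9% |
| 5%/10% | -0.075 | -0.060 | 12.6% | 8.7% |
| 10%/5% | +0.030 | +0.060 | 0.5% | not run |

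A repeat simulation gave about 3.2%, 3.8%, 5.0% and 12.8% for the first four rows without the shift. With an imputation SD of 1.0% they were 3.3%, 4.3%, 5.5% and 14.1%. For a single dose, error is 2.4% to 2.8% at equal missingness and 7.7% at 5%/10%.

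These errors are lower than a plain normal calculation gives. At 10/10 pooled that would be Φ(0.030/0.07562 - 1.960) = Φ(-1.563) = 5.9%. Rubin's rules widen the interval, and that offsets part of the bias.

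**4. Missing participants share a common mean.** Take μ between 0 and -0.6% in both arms. Then bias = (mL - mT) × μ, which is zero at equal missingness. At 5%/10% it is 0.05 × μ, between 0 and -0.030. Simulated pooled error is about 0.9% to 2.1% at equal missingness of 5% to 15%, and 1.5% to 3.9% at 5%/10%. Adding the shift at equal missingness takes it to about 0.9% to 1.0%, 0.4% to 0.5% and 0.1% at 5%, 10% and 15%.

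**5. Which case fits.** Protocol 7.2 has anyone who leaves the study stop study drug at the same time. Protocol 7.1 applies one rule on continued background treatment to both arms. Most missing week-52 values should therefore come from people off their assigned drug, which is closer to step 4. Step 3 describes people who miss the visit while still on treatment.

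**6. Price of a shifted fallback analysis.** At a true difference of 0 and 10%/10% missing, the power of that sensitivity analysis falls from about 97% to 93% (pooled) and from about 75% to 64% (single dose).

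**The case for a change.** The best case for a change is that it costs one sentence. The SAP itself thinks such a check is worth having, and writing it down before results are known avoids a later choice in an open-label trial.

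The fallback is also foreseeable. With 197 per dose, an assumed 5% to 20% stopping drug and 30% to 70% of those measured at week 52, donors per dose arm run from 197 × 0.05 × 0.3 ≈ 3 to 197 × 0.20 × 0.7 ≈ 28. The SAP narrowed the pool further: Protocol 9.4.3.1 also counted participants who had started rescue medication. Nor does the SAP say whether failure in one arm moves every arm to the fallback.

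The textual point stands in full. Its weight does not. The SAP attributes the bias to retrieved-dropout imputation; extending it to return-to-baseline is an inference, and step 4 shows that it need not hold. The size and direction of the shift are already fixed in 6.12.1.3, so an analyst has little latitude in carrying it over, and SAP 6.2 allows additional analyses. The large error figure needs lispro to lose twice as many participants as tirzepatide. The arm-specific intolerance route that the protocol describes (Protocol 6.6.3) concerns tirzepatide. Those participants are asked to stay in the study, so this does not prove higher missingness there, but nothing points the other way.

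**Conclusion.** No change is needed. This is a missing detail in a conditional branch, and analysts would fill it sensibly by applying the stated 0.3% shift to whichever imputation is primary. No decision depends on it: the noninferiority claim rests on the unshifted interval in both branches, and the efficacy-estimand analysis is untouched.

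Harm would need non-convergence, appreciable missing data although the protocol says "Discontinuation is expected to be uncommon", and an unfavourable pattern of missingness. On the pattern that best fits Protocol 7.2, return-to-baseline is already conservative at equal missingness (about 0.9% to 2.1% pooled, against 2.5%). If missing participants keep the full difference, pooled inflation is modest (about 3% to 5%) and single-dose error stays near nominal. In the one case with large inflation (12.6%), the extra sentence would still leave 8.7%, so it would not supply the protection it appears to offer.

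These sizes rest on the assumed missing fractions, a lispro change of -1.2% and zero-centred imputation, none of which the documents give. Appreciably more missing data on lispro than on tirzepatide would make the fallback result worth a closer look.
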